## 2. Abbreviations and Definitions

CSR	Clinical Study Report
CT	Computerized Tomography
dAVF	Dural Arteriovenous Fistulas
DMSO	Dimethyl Sulfoxide
DSA	Digital Subtraction Angiography/Angiogram
eCRFs	Electronic Case Report Forms
FAS	Full Analysis Set
IFU	Instructions For Use
INR	International Normalized Ratio
IRB	Institutional Review Board
MRA	Magnetic Resonance Angiography/Angiogram
MRI	Magnetic Resonance Imaging
mRS	Modified Rankin Scale
nBCA	N-Butyl-Cyanoacrylate
NIHSS	NIH Stroke Scale
PHIL	Precipitating Hydrophobic Injectable Liquid
QOL	Quality of Life
SAP	Statistical Analysis Protocol

### **3. Introduction**

This document describes the planned statistical analyses for the clinical study titled as “PHIL DAVF: Study of PHIL® Embolic System in The Treatment of Intracranial Dural Arteriovenous Fistulas” (protocol number: CL11005). This analysis plan is meant to supplement the study protocol. Any deviations from this analysis plan will be described in the clinical study report (CSR).

### **4. Study Design**

The proposed study is a prospective, multicenter, single-arm, clinical study evaluating outcomes in subjects with intracranial dural arteriovenous fistulas (dAVF) treated with PHIL® device. The purpose of this study is to evaluate the safety and probable benefit of PHIL® device for the treatment of intracranial dAVF.

#### **4.1 Primary Measured Outcomes**

The following outcomes will be measured:

- Safety: The proportion of subjects with neurological death or ipsilateral stroke within the first 30 days following completion of the first PHIL treatment procedure.
- Probable benefit: Angiographic occlusion of the pre-specified target vessel intended for treatment at procedure following completion of the first PHIL treatment procedure.

Neurologic death is subject death reported as having resulted from a neurologic cause. Stroke is defined as a new focal neurological deficit in a defined vascular distribution of abrupt onset with symptoms persisting for >24 hours AND a neuro-imaging study or other quantitative study that does not indicate a different etiology. This includes ischemic and hemorrhagic strokes.

Angiographic occlusion of the pre-specified target vessel is defined as cessation of flow at the point of embolic agent administration at the target vessel.

#### **4.2 Secondary Measured Outcomes**

The following outcomes will be measured:

- The proportion of subjects with neurological death or ipsilateral stroke within the first 30 days following completion of all PHIL treatments
- Angiographic occlusion of the pre-specified target vessel intended for treatment at procedure following completion of all PHIL treatments

- New-onset or worsening of permanent morbidity at 6 month follow-up
- New-onset intracranial hemorrhage at 6 month follow-up
- New-onset of cranial nerve palsy at 6 month follow-up
- Clinically significant technical events during the PHIL embolization procedure(s) including but not limited to reflux of embolic material, migration of the embolic material, catheter entrapment or damage, and vessel dissection.
- Device-related adverse events at procedure and within 30 days
- Device-related mortality at procedure and within 30 days
- Procedure related adverse events including complications of arterial puncture, contrast induced nephropathy, radiation-induced injuries, renal and anesthesia-related complications.
- New-onset of device/procedure-related neurological adverse event or worsening of previous neurological deficit unresolved at 6 month follow-up.

Permanent morbidity is defined as a worsening of mRS score at 6 month follow-up compared to the baseline mRS score of:

- $\geq 1$  point in subjects experiencing a stroke
- $\geq 2$  points in subjects experiencing neurological adverse events.

Note, worsening mRS scores associated with non-neurological causes, resulting in limitations to the subject's ability to walk or require assistance to attend to own bodily needs, will not be considered permanent morbidity. This includes medical events such as, bone fractures, muscle, ligament and tendon injuries, and other physical injuries.

#### 4.3 Additional Measured Outcomes

The following outcomes will be measured:

- Improvement of neurological symptoms
- Number of procedures required to treat the fistula at 6 months follow-up
- Procedure time (defined as first to last fluoroscopic or digital subtraction angiographic acquisitions)
- Radiation exposure (dosage and time)
- Injected volume of PHIL
- Modified Rankin Scale (mRS) at 3 and 6 months

- Self-reported QOL questionnaire, EQ-5D at 6 months
- Unplanned adjunctive treatments

#### **4.4 Safety Evaluation**

All adverse events will be assessed in terms of the seriousness (SAE vs non-SAE) and relationship to the study device and procedure. Unanticipated adverse device effect will be collected as well.

### **5. Investigation Plan**

The study is a prospective, multicenter, single-arm, clinical study evaluating outcomes in subjects with intracranial dural arteriovenous fistulas treated with PHIL® device. The purpose is to evaluate the safety and probable benefit of MicroVention, Inc. PHIL Liquid Embolic material for the treatment of intracranial dural arteriovenous fistulas.

The study will include up to 75 patients with an intracranial dAVF aged 22-80 years.

Subjects will undergo screening / baseline evaluation, the study procedure, supplemental embolization procedures as needed and clinical and angiographic follow-up up to 6 months.

The total subject duration is expected to be approximately 9 months.

Detailed investigational plan can be referred to the clinical study protocol (Protocol Number: CL11005).

### **6. Determination of Sample Size**

This study will enroll up to seventy five (75) subjects in this study to obtain 6 month follow-up in 60 subjects. This assumes up to fifteen (15) subjects may be lost to follow-up. No statistical justification is established.

### **7. Study Subjects**

#### **Analysis Population**

The analysis population will be comprised of the results from up to 75 treated subjects. Results will be presented based on one population:

Full Analysis Set (FAS): defined all enrolled subjects in whom the PHIL device was implanted.

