4 SELECTION AND WITHDRAWAL OF SUBJECTS

Subjects who are enrolled in the study but subsequently do not meet the pre-operative inclusion criteria below will not be treated with the PHIL and will be considered enrolled but not treated. These subjects will be considered screen failures, exited from the study, replaced with other subjects that satisfy enrollment and pre-procedural inclusion criteria and will not be included in the analyzed populations.

Before any subject is treated in the study, the screening / baseline angiogram will be reviewed by at least one of the Study Principal Investigators.

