5.6 PHIL PROCEDURE

Unless medically justified, the initial embolization procedure should be performed within 45 days of completion of the baseline assessment. The study procedure consists of pre-placement imaging, study device placement and post-placement imaging. Subjects require no special preparation for the procedure beyond standard of care for endovascular neuro-interventions. Investigators at their discretion may elect to pre-medicate with antiplatelet agents.

It is expected that the majority of PHIL initial and supplemental embolization procedures are completed under general anesthesia but a minority of procedures may be completed under conscious sedation, depending upon the center's standard of care. Heparin is administered according to standard practices. The PHIL device should be used per the IFU provided in the PHIL packaging. The PHIL procedure will be performed only by the physician investigator(s) trained by the Sponsor or its designee to perform the procedure.

The point of enrollment occurs when the PHIL liquid embolic syringe and adaptor assembly is connected to the microcatheter hub.

The investigator will record key characteristics of the device and procedure in the study's eCRF. The investigator will also record technical events/device malfunctions. Radiation exposure will be recorded as absorbed radiation dose and cumulative fluoroscopy time will be recorded. The investigator will retain and provide to the sponsor all images taken during or immediately after the study procedure (including any not specified above).

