15 DEFINITIONS

Term	Definition
Adjunctive treatment Adverse Event (AE)	Additional treatments with to continue or complete the treatment of the fistula
	other than PHIL. This could include but is not limited to other liquid embolic agents embolic coils, surgery or radiosurgery.
	Any untoward medical occurrence, unintended disease or injury, or untoward
Adverse event (AE)	clinical signs (including abnormal laboratory findings) in subjects, users or other
	persons, whether or not related to the investigational medical device. (ISC 14155:2011 3.2)
	NOTE 1: This definition includes events related to the investigational medical device
	or the comparator.
	NOTE 2: This definition includes events related to the procedures involved.
	NOTE 3: For users or other persons, this definition is restricted to events related to
	investigational medical devices.
Completion of treatment	Cessation of blood flow through all the vessels targeted for embolization, as specified by treating physician in eCRF.
Concomitant disease-related adverse event	Event is clearly attributable to the underlying concomitant disease state with no
	temporal relationship to the device, treatment, or medication.
Device-related adverse event	Event has a strong temporal relationship to the study device, and alternative
	etiology is less likely.
Enrolled	Subject has provided written informed consent to participate in the study, meets
	all enrollment criteria, and treatment with the PHIL device is attempted. The point
	of enrollment occurs when the PHIL liquid embolic syringe and adaptor assembly is
	connected to the microcatheter hub.
Full Analysis Set Population (FAS)	All enrolled subjects including only those in whom the PHIL™ device was implanted.
NIH Stroke Scale (NIHSS)	Tool to quantify neurological impairment caused by stroke.
Intracranial hemorrhage	Hemorrhage within the fixed vault of the cranium (skull)
Mild	No limitation of usual activities, no therapy or only symptomatic therapy required
(AE severity)	to treat the injury or illness.
Moderate	Some limitation of usual activities or specific therapy is required.
(AE severity)	Some illitation of assault activities of specific therapy is required.
Modified Rankin Scale (mRS)	Scale for measuring general neurologic function.
,	0 No symptoms at all
	1 No significant disability despite symptoms; able to carry out all usual duties
	and activities
	2 Slight disability; unable to carry out all previous activities, but able to look

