	after own affairs without assistance
	3 Moderate disability; requiring some help, but able to walk without assistance
	4 Moderately severe disability; unable to walk without assistance and unable
	to attend to own bodily needs without assistance
	5 Severe disability; bedridden, incontinent and requiring constant nursing care
	and attention
	6 Dead
Neurologic death	Subject death reported as having resulted from a neurologic cause.
Procedure	The index study procedure involving the placement of the PHIL™ device.
Procedure-related adverse event	Event has a strong temporal relationship to any PHIL procedure. This includes AEs
Troccuure-relateu auverse event	attributable to any device(s) other than the PHIL™ device used at any PHIL procedure, such as access devices, delivery microcatheters, non-ionic contrast,

	guidewires, or any other adjunctive, approved/cleared device for treatment of intracranial dAVFs.
Dracodura tima	Start: Time of first fluoroscopic or digital subtraction angiographic acquisition
Procedure time	
	End: Time of last fluoroscopic or digital subtraction angiographic acquisition
Screen Failure	Screened patient who did not meet the enrollment criteria and was not enrolled in
	the study.
Serious Adverse Event (SAE)	An adverse event that:
	a) Led to death,
	 b) Led to serious deterioration in the health of the subject, that either resulted in
	a. A life-threatening illness or injury, or
	b. A permanent impairment of a body structure or a body function, or
	c. In-subject or prolonged hospitalization, or
	 d. Medical or surgical intervention to prevent life-threatening illness or injury or permanent impairment to a body structure or a body function,
	Led to fetal distress, fetal death or a congenital abnormality or birth defect (ISC 14155:2011 3.37)
	NOTE: Planned hospitalization for a pre-existing condition, or a procedure required
	by this protocol, without serious deterioration in health, is not considered a serious
	adverse event.
Severe	Inability to carry out usual activities, hospitalization, emergency treatment, life
(AE severity)	threatening events, or death.
Stroke	Stroke – A new focal neurological deficit in a defined vascular distribution of abrupt
	onset with symptoms persisting for > 24 hours AND a neuro-imaging study or other
	quantitative study that does not indicate a different etiology.
Study disease-related adverse	Event is clearly attributable to the underlying study disease state with no temporal

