#### **8.5 Duration Variables**

Study Day 1 is the day of study device deployment (index procedure). Study day will appear in the listings where applicable and is calculated relative to day 1 using the general formula:

Study Day = (Date of Event – Date of Study Device Deployment) +1, if event date is on or after Date of Study Device Deployment

Study Day = (Date of Event – Date of Study Device Deployment), if event date is before the Date of Study Device Deployment

Duration variables will be calculated using the general formula:

$$[(\text{end date} - \text{start date})] + 1$$

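### The only analysis set requires PHIL to have been implanted, so a subject enrolled at syringe connection but never implanted enters no reported rate

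*SAP*

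**What the plan says.** SAP section 7 and Protocol 8.3 use identical words for the single population on which results are presented: "Full Analysis Set (FAS): defined all enrolled subjects in whom the PHIL device was implanted". Protocol section 15 is more restrictive in tone but the same in substance: "All enrolled subjects including only those in whom the PHIL™ device was implanted".

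Enrollment is a separate and earlier event. Protocol 5.6 states: "The point of enrollment occurs when the PHIL liquid embolic syringe and adaptor assembly is connected to the microcatheter hub". The definition of an enrolled subject in Protocol section 15 adds consent, the enrollment criteria, "and treatment with the PHIL device is attempted". It does not require that any PHIL be delivered.

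SAP 8.2 and 8.3 report each primary and secondary outcome as a count, a number evaluated, a percentage and Clopper-Pearson 95% limits. SAP 8.1 expresses adverse event counts as a proportion of the population, promises listings of all recorded data, and mentions subject disposition.

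The time references all assume that PHIL was placed. The 30-day safety window starts at completion of the first PHIL treatment procedure (SAP 4.1). Protocol section 15 defines a procedure as "The index study procedure involving the placement of the PHIL™ device". The Study Day formula in SAP 8.5 counts from the date of device deployment.

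**The concern.** Connection comes before injection, so an eligible subject can be enrolled and then receive no PHIL. That subject falls outside the FAS, and no second population exists to pick them up.

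Three consequences follow. A failed attempt does not count against the benefit rate. A primary safety event in such a subject does not reach the primary safety rate. A clinically significant technical event between connection and first injection is lost from the rate meant to count such events. The status of these subjects and their Day 1 are also unstated, so even an analyst who wished to include them would have to invent a rule after seeing the data. SAP 8.1 foresees comparison with published rates where applicable, which is a further reason to make the denominator explicit.

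**Working it through.** **Step 1: the plan's own figure.** Protocol 8.1 and SAP section 6 enroll up to 75 to obtain 6-month follow-up in 60, allowing for 15 lost. 15/75 = 20%, and 60/(1 − 0.20) = 75, so the figure reproduces. Both documents say that no statistical justification is established, so there is no power or test to recompute.

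**Step 2: does anything return these subjects to a rate?**
- SAP 8.1: listings and possibly disposition show them; adverse event percentages use the single population.
- SAP 8.2 to 8.4: no other denominator is named.
- SAP 8.5: Day 1 needs a deployment date.
- SAP 8.6: the imputation rules deal with missing outcomes and create no second population.

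Nothing does.

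**Step 3: benefit.** Let N be the number enrolled, k the number enrolled but not implanted, and x the occlusions. None of the x can come from the k. The FAS rate is x/(N − k) and the all-enrolled rate is x/N, so the FAS rate is never the lower of the two. The documents give no k. Assumptions: N = 75, k = 1 to 3, and x = 45, chosen to match the protocol's expectation of about 60%. Intervals are Clopper-Pearson 95%.

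| k | FAS | All enrolled | Difference |
|---|---|---|---|
| 0 | 45/75 = 60.0% (48.0 to 71.1) | 45/75 = 60.0% | 0 |
| 1 | 45/74 = 60.8% (48.8 to 72.0) | 45/75 = 60.0% | 0.8 points |
| 2 | 45/73 = 61.6% (49.5 to 72.8) | 45/75 = 60.0% | 1.6 points |
| 3 | 45/72 = 62.5% (50.3 to 73.6) | 45/75 = 60.0% | 2.5 points |

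The interval at 45/75 is 71.1 − 48.0 = 23.1 points wide.

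**Step 4: safety.** With e events among all enrolled, of which d are in omitted subjects, the FAS rate is (e − d)/(N − k). Assume e = 11, so 11/75 = 14.7% (7.6 to 24.7), close to the protocol's expected ceiling of about 15%. At k = 1 the FAS gives 11/74 = 14.9% (7.7 to 25.0) if the omitted subject had no event, and 10/74 = 13.5% (6.7 to 23.5) if they had one. The direction is not fixed.

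**Step 5: technical events.** Assume 5 subjects with events among those implanted, and k = 3. The FAS gives 5/72 = 6.9%. All enrolled gives from 5/75 = 6.7%, if no omitted subject had a qualifying event, to 8/75 = 10.7%, if every one did. The upper figure is a bound, not an expectation.

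**The case against.** The strongest defense is that a treated-subject set suits a descriptive single-arm study. Benefit is defined as cessation of flow where the agent was administered, and both documents describe the population as treated subjects. Counting failed attempts answers a different question, about attempting PHIL. That is fair, and it is why the FAS should stay. It does not justify leaving the attempt-based rate unreported when enrollment itself is defined by attempt.

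The defense is also right that data and oversight are not missing. Protocol 7.1 collects adverse events from enrollment until study exit and follows them to resolution or the end of the 6-month follow-up. Technical events must be reported, deaths go to the FDA, and an independent committee adjudicates the primary and secondary outcomes. What is missing is a tabulated rate.

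A reader might go further in three ways that the documents do not support.
- **That Protocol section 4 removes and replaces failed attempts.** It says "These subjects will be considered screen failures, exited from the study, replaced with other subjects", but only of subjects who turn out not to meet the pre-operative inclusion criteria. An eligible subject with a failed attempt is not covered, so their status is unstated rather than contradictory. Nor do the documents support a scenario in which such subjects are replaced and more than 75 are enrolled.
- **That every technical event preventing treatment is lost.** Reflux and migration require PHIL to have been injected. Access failures found at the procedure are late screening failures under Protocol 5.5.2, and damage before connection precedes enrollment, so an all-enrolled set would miss it too. Only the interval from connection to first injection is affected.
- **That safety is biased downward.** Step 4 shows that it can move either way.

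On the time origin, SAP 8.5 does gloss deployment as the index procedure. That hints at an answer, but the formula still needs a deployment date.

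**Conclusion.** The gap is real and follows from the definitions alone: enrollment requires an attempt, the only analysis set requires implantation, and no section bridges the two. The benefit rate can only be raised or left unchanged. On the assumptions above the rise is about 0.8 points per subject, 0.8 to 2.5 points for 1 to 3 subjects, which is small beside a 23-point interval. It is zero if every enrolled subject is implanted, and subjects who receive some PHIL without occlusion remain in the FAS as failures. No test, power or decision rule is affected. This is a cheap improvement to the reported percentages and does not call the trial's conclusions into question. Confidence is high in the definitional gap; the size rests on an assumed k and assumed event counts.

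**What to change.** - Keep the FAS. In SAP section 7 and Protocol 8.3 add an all-enrolled (PHIL attempted) set. Report both primary outcomes and the clinically significant technical-event rate on it beside the FAS, counting subjects with no PHIL implanted as non-occluded.
- Say what counts as implanted, which neither document does. Report the number enrolled but not implanted, with reasons. If it is zero, say so; the two sets are then identical.
- For these subjects, use the date of the attempted index procedure as Study Day 1 and as the origin of the 30-day safety window. Adverse event collection stays as Protocol 7.1 already provides.
- Separately, reconcile Protocol section 4, which calls certain subjects enrolled but not treated and treats them as screen failures, with Protocol 5.6 and section 15, where a screen failure is a "Screened patient who did not meet the enrollment criteria and was not enrolled in" the study.

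The cost is some wording in both documents, one extra table column, and a reported benefit rate on the added set that may be slightly lower than on the FAS.

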## 8. Statistical Analysis Methodology

### 8.1 General Statistical Approach

Descriptive statistics (mean, standard deviation, frequency charts, etc.) for baseline participant characteristics, subject disposition and other relevant study parameters will be reported. Where applicable, a comparison to rates reported in the scientific literature will be performed.

Tabulations of summary statistics, graphical presentations, and statistical analyses will be performed using SAS. The statistical analyses will be based on data pooled across sites in aggregate. All subset summary tables and data listings will be sorted by site and subject. The pre-procedure observations will be used as the baseline value for calculating post-procedural changes from baseline.

Continuous demographic parameters, such as the age of the subject at the time of enrollment, will be summarized using descriptive statistics (N, mean, median, standard deviation, minimum and maximum value). Categorical demographic parameters, such as gender, will be summarized as a proportion of the population.

Data obtained during the neurological examination using the Modified Rankin and self-reported EQ-5D will be summarized at each time point using descriptive statistics.

Routine clinical chemistry and hematology will be assessed by the investigator as normal/abnormal and not clinically significant/clinically significant. The incidence of abnormal and clinically significant values will be summarized and reported in frequency tables for each visit at which the data are collected.

Subject counts will be tabulated for all adverse events for the population. Adverse events will also be tabulated for events that occurred from the start of the procedure to 6 month follow-up after last embolization. Tabulated subject counts will be presented as a proportion of the population.

All recorded data will be presented in the individual data listings.

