5.5.3 Pre-Procedure Assessment

Routine clinical chemistry and hematology labs will need to be collected from the subject, this may be obtained between baseline and pre-procedure. Within 7 days preceding the index procedure, the subject must complete self-reported QOL questionnaire using EQ-5D.

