5.8 Supplemental PHIL procedure

Complete treatment of the target dAVF may require one or more PHIL procedures. Additional procedure(s) are to be scheduled and performed at the treating physician's discretion. It is estimated that up to seven (7) PHIL procedures may be required to treat the fistula. The physician shall determine the number of treatment procedures based on factors specific to each patient, such as dAVF size, number of feeders, fistulous connections, and location relative to eloquent territory. The treating physician should discontinue PHIL treatment if reflux into an eloquent artery is observed during the procedure.

The supplemental PHIL procedure consists of pre-procedure physical exam to assess dAVF symptoms, collection of routine clinical chemistry and hematology labs pre-procedure, pre-placement imaging, study device placement and post-placement imaging. Subjects require no special preparation for the procedure beyond standard of care for endovascular neuro-interventions. Investigators at their discretion may elect to pre-medicate with antiplatelet agents.

It is expected that the majority of PHIL initial and supplemental embolization procedures are completed under general anesthesia but a minority of procedures may be completed under conscious sedation, depending upon the center's standard of care. Heparin is administered according to standard practices. The PHIL device should be used per the IFU provided in the PHIL packaging. The supplemental PHIL procedure will be performed only by the physician investigator(s) trained by the Sponsor or its designee to perform the procedure.

The investigator will record key characteristics of the device and procedure in the study's eCRF. The investigator will also record technical events/device malfunctions. Radiation exposure will be recorded as absorbed radiation dose and cumulative fluoroscopy time will be recorded. The investigator will retain and provide to the sponsor all images taken during or immediately after the study procedure (including any not specified above).

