### **8.3 Secondary Measured Outcomes**

The descriptive analysis of the following secondary measured outcomes will include the number of subjects with the outcomes of interest, the total number evaluated, the percent, and the Clopper-Pearson two-sided 95% confidence limits on the percent.

- The proportion of subjects with neurological death or ipsilateral stroke within the first 30 days following completion of all PHIL treatments
- Angiographic occlusion of the pre-specified target vessel intended for treatment at procedure following completion of all PHIL treatments
- New-onset or worsening of permanent morbidity at 6 month follow-up
- New-onset intracranial hemorrhage at 6 month follow-up
- New-onset of cranial nerve palsy at 6 month follow-up
- Clinically significant technical events during the PHIL embolization procedure(s) including but not limited to reflux of embolic material, migration of the embolic material, catheter entrapment or damage, and vessel dissection.
- Device-related adverse events at procedure and 30 days
- Device-related mortality at procedure and 30 days
- Procedure related adverse events including complications of arterial puncture, contrast-induced nephropathy, radiation-induced injuries, renal and anesthesia-related complications.

- New-onset of device/procedure-related neurological adverse event or worsening of previous neurological deficit unresolved at 6 month follow-up.

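### Laboratory safety is summarised only as per-visit counts of abnormal values, so the planned tables cannot show how many subjects became newly abnormal after PHIL treatment

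*SAP*

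**What the plan says.** SAP 8.1 sets the grading: "Routine clinical chemistry and hematology will be assessed by the investigator as normal/abnormal and not clinically significant/clinically significant". It then sets the output: "The incidence of abnormal and clinically significant values will be summarized and reported in frequency tables for each visit". Protocol 8.2 carries the same text. Neither document names a laboratory shift table, a change-from-baseline summary, or a rule for what counts as a new abnormality.

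Two other sentences in SAP 8.1 bear on the point. One is a general baseline rule that does not exclude laboratory data: "The pre-procedure observations will be used as the baseline value for calculating post-procedural changes from baseline". The other concerns listings: "All recorded data will be presented in the individual data listings".

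The samples needed for a within-subject comparison are already required:

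- Before the first procedure (Protocol 5.5.3): "Routine clinical chemistry and hematology labs will need to be collected from the subject, this may be obtained between baseline and pre-procedure".
- Before discharge after each procedure (Protocol 5.7 and 5.8.1).
- Before each supplemental procedure (Protocol 5.8): "collection of routine clinical chemistry and hematology labs pre-procedure". The same section estimates that up to seven PHIL procedures may be needed.
- At 30 days, 3 months and 6 months after the last PHIL treatment (Protocol 5.9).

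Renal events also appear in a secondary outcome, as adverse events (SAP 8.3): "Procedure related adverse events including complications of arterial puncture, contrast-induced nephropathy, radiation-induced injuries, renal and anesthesia-related complications".

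**The concern.** The plan calls its per-visit counts an incidence. An incidence counts subjects who did not have the abnormality at the start and then developed it. A count of everyone abnormal at a visit also includes those who were abnormal before PHIL was used, which makes it a prevalence. A stable, long-standing abnormality is counted again at every visit. A new abnormality in one subject can be offset by another subject's return to normal, leaving the table unchanged.

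What is at stake is what the laboratory section of the study report can say. Subjects give blood before treatment and at several later points, and Protocol 5.13 classes the 30-day and 3-month samples as study-specific. Readers will want to know how many subjects developed a laboratory abnormality after PHIL. Followed as written, the tables do not answer that.

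**Working it through.** **Inputs.** The documents give no laboratory abnormality rates and no laboratory figure to reproduce. The only figure available is the sample size (Protocol 8.1, SAP 6), which supplies N: 60 / (1 − 15/75) = 60 / 0.80 = 75, matching the stated 75. The abnormality rates below are assumptions, shown over a range.

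**What two per-visit counts reveal.** Take one analyte and N subjects with both samples. Let b be the number abnormal before the procedure, a the number abnormal at a later visit, and x the number normal before and abnormal later.

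- Those abnormal later are either new (x) or were abnormal at both times. The second group cannot exceed b, so x ≥ a − b. Also x ≥ 0.
- New cases cannot exceed a, and they can come only from the N − b subjects who were normal before.
- Hence max(0, a − b) ≤ x ≤ min(a, N − b).

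| N | Abnormal before (b) | Abnormal later (a) | Possible new cases (x) | As % of N |
|---|---|---|---|---|
| 75 | 8 (10%) | 8 (10%) | 0 to 8 | 0% to 10.7% |
| 75 | 15 (20%) | 15 (20%) | 0 to 15 | 0% to 20.0% |
| 75 | 22 (30%) | 22 (30%) | 0 to 22 | 0% to 29.3% |
| 75 | 15 (20%) | 22 (30%) | 7 to 22 | 9.3% to 29.3% |
| 75 | 22 (30%) | 15 (20%) | 0 to 15 | 0% to 20.0% |
| 60 | 12 (20%) | 12 (20%) | 0 to 12 | 0% to 20.0% |

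(10% and 30% of 75 are 7.5 and 22.5, taken as 8 and 22.)

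In the second row, for example, max(0, 15 − 15) = 0 and min(15, 75 − 15) = 15. Either the same 15 subjects are abnormal throughout and none is new, or all 15 have normalised and 15 others have become abnormal. The planned table is identical in both cases. The same bounds apply if only clinically significant values are counted. Cross-classifying each subject's earlier and later grade replaces the range with one exact number.

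**Which sample is the baseline.** For a subject with two PHIL procedures the samples run: before procedure 1, discharge 1, before procedure 2, discharge 2, 30 days, 3 months, 6 months. Suppose an abnormality appears after procedure 1 and is still there before procedure 2. At 30 days it is new against the first pre-procedure sample but unchanged against the second. SAP 8.1 speaks only of pre-procedure observations. The Protocol's definitions section ties the term procedure to the index procedure, and SAP 8.5 counts study days from it, but neither states the rule for laboratory data. A shift table needs that rule.

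**The case against.** The strongest reply is that the plan already has the pieces. SAP 8.1 has a general pre-procedure baseline rule that covers laboratory data by default. The pre-procedure sample is a collection point, so it should have its own column of counts. All recorded data are to be listed, so anyone can build a shift from the listed grades. The clinical-significance grade filters out trivial out-of-range results. The study is single-arm and descriptive, with no hypothesis test.

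Most of this stands as a limit on the size of the point. A reader might infer that the pre-procedure sample is ignored, or that new abnormalities cannot be derived at all. The documents support neither reading: the baseline rule exists and the subject-level data will be available. What the reply does not supply is the output. No laboratory table uses the baseline rule, a listing of up to 75 subjects is not a pre-specified summary, and a clinically significant abnormality present before treatment is still counted at later visits.

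A reader might also infer that contrast-induced nephropathy will be under-counted. The documents do not show this. It is a component of an adverse event outcome and is not derived from the laboratory tables. The adverse event definition covers abnormal laboratory findings (Protocol 7.2.1), deterioration from screening status may be recorded (Protocol 7.1), events observed by the investigator are recorded at each follow-up visit as well as those the subject reports (Protocol 5.9), and secondary outcomes are adjudicated (Protocol 7.4).

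Nor do the documents support adding a laboratory threshold for nephropathy. They name no analyte, cut-off or time window, and they do not say whether numeric values are held. The post-procedure sample is due only before discharge, with no fixed interval. A threshold would also turn an adverse event outcome into a laboratory one.

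**Conclusion.** The point holds as a gap in the planned tables. Per-visit counts of abnormal and clinically significant values are prevalences labelled as incidence, and they leave the number of newly abnormal subjects undetermined. With 15 of 75 abnormal before and after, that number lies anywhere from 0 to 15 (0% to 20%); at other assumed rates the range moves as tabulated above.

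The rates are illustrative and the bounds are per analyte. The conclusion also assumes that a grade is recorded for each pre-procedure and post-procedure sample, as SAP 8.1 implies. A shift table would show change over time within subjects. Without a control arm it would not show that PHIL caused the change. The matter touches no primary outcome, and the improvement is worth making mainly because it is nearly free.

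**What to change.** In SAP 8.1:

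1. Add within-subject shift tables for each analyte with three grades (normal; abnormal, not clinically significant; abnormal, clinically significant), from the pre-procedure sample to discharge, 30 days, 3 months and 6 months. Use subjects with both samples and state how many lack one.
2. Report as the incidence the subjects whose grade is new or worsened, meaning normal to either abnormal grade, or not clinically significant to clinically significant.
3. Keep the per-visit counts but label them prevalence.
4. State which sample is the baseline when there are several PHIL procedures. One workable rule is the last sample before the procedure concerned for discharge, and the sample before the first procedure for the follow-up visits. Say also how several discharge samples from one subject are shown.

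Make the matching edit in Protocol 8.2 if it is revised again. This needs no new blood draws and uses grades already planned; the cost is a few extra tables and their programming.

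As a lesser suggestion, the sponsor could state how contrast-induced nephropathy is identified within the procedure-related adverse event outcome, so that sites and adjudicators apply one definition. No threshold is proposed here.
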